- Treatment emergent serious adverse events as characterized by type, frequency, severity, timing, seriousness and relationship to study treatment through Day 43.
- Treatment emergent adverse events as characterized by type, frequency, severity, timing, seriousness and relationship to study treatment through Day 8.
- Treatment emergent laboratory abnormalities as characterized by type, frequency, and severity through Day 4 (or discharge).
- Physical examination changes through Day 8 (or discharge).
- Vital sign changes through Day 8 (or discharge).
- Electrocardiogram (ECG) results through Day 8 (or discharge).

Secondary Endpoints:

- Changes in activated partial thromboplastin time (aPTT) and prothrombin fragment 1+2 (PF1+2) after dosing with PF-05230907 through Day 2.
- Anti-drug antibody/neutralizing antibody (ADA/NAb) and Factor X activity through Day 43 and/or Day 91 follow-up visit.

Exploratory Endpoints:

- ICH absolute and percent change from baseline volume at 24 hours (see Schedule of Activities [SOA]).
- PF-05230907 concentration in plasma.

- Changes in other exploratory biomarkers that may reflect pharmacologic effect of PF-05230907 or ICH progression may be evaluated.
- Potential biomarkers of neuro-inflammation and/or neurological outcomes to better understand ICH and/or its outcomes.
- Computed tomography (CT) parameters that may inform future investigations of PF-05230907 and/or the condition of ICH.
- Anti-Chinese hamster ovary (CHO) protein antibodies.
- Anti-paired basic amino acid cleaving enzyme (PACE) furin antibodies.
- Neurologic function as assessed by the NIHSS.
- Surrogate measures for health resource utilization, may include duration of stay in stroke/intensive care unit (ICU), duration of hospital stay, duration of inpatient rehabilitation, and duration of outpatient rehabilitation.

Study Design:

This study employs a modified continual reassessment method (mCRM) design to estimate the MTD, defined as a target toxicity rate of 15% based on the treatment emergent thromboembolic and/or ischemic events (TIEs). The mCRM design utilizes Bayesian methodology to continuously learn the dose-toxicity relationship, which is characterized by a parametric model. The details of this design are described in the [statistical method](#) section of this protocol.

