6.3. Follow-up Visits

A study site should make every effort to have the subject attend the follow-up office/clinic visits, including arranging transportation if feasible (Day 43 and Day 91). If a subject is unable to attend the Day 43 and/or Day 91 study visit, or attend a scheduled remote visit on these days, a telephone follow-up for collection of serious adverse events since the last visit should occur if permitted per local, state, and institutional guidance.

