6.3.1. Day 43 (±7 Days)

The following procedures will be completed:

- Collect the following blood samples:
 - Immunogenicity sample collections (ADA, NAb, FX activity, Anti-CHO and Anti-PACE) for shipment to a central laboratory.
- Conduct the mRS.
- Conduct the NIHSS.
- Document birth control utilized through the protocol required 28 days after the single dose of investigational product for male subjects who are able to father children and are sexually active and at risk of pregnancy, see [Section 4.4](#).
- Monitoring of serious adverse events.
- Monitoring of concomitant medications and treatments.
- Collect appropriate health resource utilization information which includes: as applicable, date subject began in-patient rehabilitation, discharge date subject completed in-patient rehabilitation, date subject began out-patient rehabilitation, and discharge date subject completed out-patient rehabilitation.

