6.3.2. Day 91 (±7 Days)

The following procedures will be completed:

- Collect the following blood samples **only** if subject tested positive for antibody immune response to PF-05230907 at Day 43 (sites will be notified if a subject has evidence of a previous antibody immune response to PF-05230907):
 - Immunogenicity sample collections (ADA, NAb, and FX activity) for shipment to a central laboratory.
- Conduct the mRS.
- Conduct the NIHSS.
- Collect appropriate health resource utilization information which includes: as applicable, date subject began out-patient rehabilitation, and discharge date subject completed out-patient rehabilitation.

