8.2. Reporting Period

For SAEs, the active reporting period to Pfizer or its designated representative begins from the time that the subject provides informed consent, which is obtained prior to the subject's participation in the study, ie, prior to undergoing any study-related procedure and/or receiving investigational product, through and including 42 calendar days post-dose (Day 43) after the last administration of the investigational product. SAEs occurring to a subject after the active reporting period has ended should be reported to the sponsor if the investigator becomes aware of them; at a minimum, all SAEs that the investigator believes have at least a reasonable possibility of being related to investigational product are to be reported to the sponsor.

SAEs should be recorded on the case report form (CRF) from the time the subject has signed the informed consent document through 42 days post-dose (Day 43).

AEs should be recorded on the case report form (CRF) from the time the subject has taken at least 1 dose of investigational product through 7 days post-dose (Day 8).

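### SAEs are a primary endpoint through Day 43, but a subject seen early for the Day 43 visit who then attends Day 91 has no scheduled SAE question for up to the last 7 days

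*Protocol*

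**What the plan says.** Protocol 2.2 and the Protocol Summary list among the primary endpoints "Treatment emergent serious adverse events as characterized by type, frequency, severity, timing, seriousness and relationship to study treatment through Day 43". SAP 3.1.2 repeats this.

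Protocol 8.2 sets the active SAE reporting period to match: "through and including 42 calendar days post-dose (Day 43) after the last administration of the investigational product". CRF recording of SAEs closes on the same day.

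The Day 43 visit (Protocol 6.3.1) has a window of 7 days either side, and its procedure list includes "Monitoring of serious adverse events". The Day 91 list (Protocol 6.3.2) has conditional immunogenicity samples, mRS, NIHSS and out-patient rehabilitation dates, but no SAE item. The SAE row of the Schedule of Activities ends in the Day 43 column.

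For a subject who cannot attend Day 43 and/or Day 91, Protocol 6.3 says that "a telephone follow-up for collection of serious adverse events since the last visit should occur", where local rules permit.

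**The concern.** The endpoint closes on a fixed day, but the last scheduled SAE question may come a week earlier. A subject seen on Day 36 is fully compliant, and nothing scheduled afterwards asks about Days 37-43 if that subject attends Day 91.

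Two features suggest an oversight:

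- **Day 8 is handled differently.** Protocol 6.2.9 requires a Day 8 telephone call for AEs and SAEs when a subject is discharged earlier. Early Day 43 attenders get no equivalent call.
- **Ascertainment is inverted.** A subject who misses Day 91 is asked about SAEs since the last visit; one who attends is not.

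The SAP summarises SAEs as numbers and percentages of subjects by dose group (SAP 6.1.2, 6.6.1), with data taken as observed (SAP 5.4.1). A subject not asked about the final days counts in the denominator as if followed to Day 43, so any missed event lowers the reported SAE frequency. With cohorts of 3, one subject is 33 percentage points at a dose level that has a single cohort.

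**Working it through.** **Day convention.** SAP 5.3.3.1 makes the dosing day Day 1, so 42 days post-dose is Day 42 + 1 = 43, as Protocol 8.2 states. The hours in SAP Table 4 follow the same convention (1296 hr ÷ 24 = 54 days, which is Day 55, as printed).

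**Largest gap inside the protocol window.**
- Earliest compliant visit: 43 − 7 = Day 36.
- Days without a scheduled SAE question: Days 37-43, which is 7 of 42 = 16.7%.

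**Average gap, assuming visits spread evenly over Days 36 to 50.** Half the visits fall before Day 43, with a mean gap of 3.5 days; the rest have no gap. The mean is 0.5 × 3.5 = 1.75 days, or 1.75/42 = 4.2% of the period.

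**Chance that a first SAE falls in the unasked days.** The documents give no SAE rate for this period, so I assume a 42-day SAE risk r of 20%, 30% or 50% and a constant hazard h = −ln(1 − r)/42.

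- Subject seen on Day 36: exp(−35h) − exp(−42h).
- Visits evenly spread: ½ × (1 − r) × [(exp(7h) − 1)/(7h) − 1]. This averages the same expression over gaps of 0 to 7 days, for the half of subjects seen early.

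| Assumed r | 7h | Seen on Day 36 | Visits evenly spread | Expected among 21 subjects | Expected among 51 subjects |
|---|---|---|---|---|---|
| 20% | 0.0372 | 3.0% | 0.75% | 0.16 | 0.38 |
| 30% | 0.0594 | 4.3% | 1.06% | 0.22 | 0.54 |
| 50% | 0.1155 | 6.1% | 1.50% | 0.32 | 0.77 |

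The 21 is the enrolment at which the sponsor decided to stop (SAP Section 1); the 51 is the planned maximum. All figures assume that early attenders go on to attend Day 91 and that no other route captures the event. They are therefore upper figures for these assumptions.

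**Effect of the fix.** A question on or after Day 43 that covers the time since the last SAE enquiry cuts the gap to 0 days.

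**The case against.** The strongest reply is that SAE collection is continuous and does not depend on visits. The Schedule shows it as ongoing, and the duty in Protocol 8.2 runs through Day 43 whatever the visit date. Protocol 8.13 says that subjects are questioned about AEs. Sites must also obtain approval for release of health care information specifically to help collect SAEs through Day 43 (Schedule footnote l; Protocol 6.2.8 and 6.2.9). Hospital admissions tend to show in records, and a subject who has died cannot attend Day 91 and so comes to notice.

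Much of this stands. A reader might infer that SAEs on Days 37-43 cannot be captured, or rest on spontaneous reports alone. The documents do not support that: the records route is tied to Day 43 itself. But none of these provisions fixes a contact on or after Day 43, and 8.13 gives no time point. The Day 91 items would not reliably reveal a readmission either, since 6.3.2 limits resource use there to out-patient rehabilitation dates. Protocol 5.7 has subjects asked about treatments at each visit, which might prompt a report, but 6.3.2 does not list it.

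A reader might also take the Day 31 start of the extended Day 43 window in SAP Table 4 as a gap of 12 of 42 days. That does not follow. SAP 5.4.5 uses those windows to decide which out-of-window results enter by-visit summaries. SAEs are dated by onset, and a Day 31 visit is outside the protocol window.

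It may be said that actual follow-up can be recovered from the last-contact date in SAP 5.4.4.2. That derivation counts mRS and NIHSS dates, so a Day 91 attender would appear followed to Day 91 without having been asked about SAEs.

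**Conclusion.** The gap is real, runs in one direction and is small. It affects only subjects seen on Days 36-42 who then attend Day 91, and mainly non-fatal SAEs that reach neither the site nor the released records. At most 7 of 42 days go without a scheduled question; the average is about 1.75 days if visits are evenly spread.

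Under even spread, constant hazard and an assumed 42-day risk of 20% to 50%, 0.75% to 1.5% of subjects would have a first SAE in those days before backstops, or 0.16 to 0.32 subjects among 21. The figure would be lower if SAEs cluster early, which is plausible after a single dose in acute ICH. The 3.0% to 6.1% range applies only to subjects actually seen on Day 36 and should not be read as a trial-wide loss.

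Two further inferences are not supported. Dose finding is unaffected, because TIEs and the MTD rest on data through Day 8. Nor do the documents show that visit timing differs between dose groups, so a distorted dose comparison is only a possibility. This is a cheap improvement to a descriptive primary safety endpoint.

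**What to change.** Either of two protocol changes closes the gap:

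1. In Protocol 6.3.2 and the Schedule of Activities, add to the Day 91 visit the collection of any SAE with onset through Day 43 not already captured.
2. Where the Day 43 visit was held early, add a telephone call on or after Day 43, mirroring the Day 8 call.

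In SAP 6.1.2, report by dose group the number of subjects with SAE follow-up through Day 43, based on the last contact at which SAEs were asked about or records reviewed, not on the general last-contact date.

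The cost is one question or one call per early attender, and one SAP line. The drawback of the Day 91 option is recall: from Day 91 back to Days 43-37 is 48 to 54 days, about 7 to 8 weeks, and somewhat longer if that visit is late. The call avoids this. If follow-up was already complete when the study was terminated, the protocol change has little left to act on, but the SAP line still applies.

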 - The following medical history elements affect study eligibility and **must** be collected during the screening period: non-ICH related severe uncontrolled medical conditions, other severe acute and chronic medical and psychiatric conditions and laboratory abnormalities that may increase the risk associated with study participation; ischemic, vaso-occlusive and thrombotic events or conditions; prothrombotic disorders; thrombocytopenia; coagulopathy, acute sepsis, crush injury, and disseminated intravascular coagulation events or conditions; and hamster protein allergies.
 - Concomitant medications taken within 7 days of study enrollment that do not affect eligibility. The following concomitant medication information affects study eligibility and **must** be collected during the screening period: oral anti-coagulant(s) [eg, warfarin or novel oral anticoagulant], low molecular weight heparin and heparin (except when used as catheter flush).
 - Concomitant treatments within 7 days of study enrollment that do not affect eligibility.
 - Doppler lower extremity ultrasonography.
 - NIHSS.
- f. If during hospital confinement period, the magnitude of a vital sign abnormality is sufficient to be reported as an AE then vital signs should be collected as a daily unscheduled observation during the hospital confinement period (eg, Day 5 through Day 8/discharge) and should be followed until the AE resolves or stabilizes-see [Section 8.1](#).
- g. The highest observed blood pressure result for each of the following Day 1 post-dose time intervals to be collected: hour 0-3, hour 3-6, hour 6-12, and hour 12-24 for a total of 4 collected highest observed BP results.
- h. Subject reported weight measured within the last 3 months is acceptable if actual weight cannot be obtained. If subject reported weight is utilized, actual weight should be collected as soon as possible post-dose. Subject reported height is acceptable.

- i. CT scan is the preferred imaging modality however for the Day 4 assessment a site may substitute an MR scan based on local standard of care (SoC), local regulatory, or clinical considerations at the investigator's discretion.
- j. ADA, NAb and FX activity to be collected at Day 91 only if subject tested positive for antibody immune response at Day 43.

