Treatment emergent changes in clinical safety laboratory values were generally small and sporadic, with no clinically significant changes in hematology including platelet count, PT/INR, fibrinogen, ATIII, cardiac troponin I, or D-dimer (Day 7 and on). Dose dependent modulation of Protein C and Protein S activity, when analyzed with a clot based assay, were observed. Non-clinical studies indicate these changes reflect pharmacologic activity of the drug.⁶ Protein C activity and free Protein S level measured using non-clot-based assays for the 3 and 5 $\mu\text{g}/\text{kg}$ dose groups showed no treatment-related reduction. No subject had an adverse event (AE) related to abnormal laboratory test results and no subject met the pre-specified stopping rule criteria.

One weak and transient anti-drug antibody (ADA) response was detected in one subject from the 3 $\mu\text{g}/\text{kg}$ cohort at a single time point of Day 29. ADA results for the same subject on Day 1 (baseline), Day 15, Day 43, and the 6 month follow-up were negative. The positive anti-drug antibody did not cross react with native factor X or factor Xa and had no neutralizing activity. Based on all the available data, the sponsor, investigator, and the study eDMC determined that this finding did not alter the benefit risk profile of PF-05230907 for the intended indication of intracerebral hemorrhage.

Based on the PK data for all the subjects enrolled in the study, peak plasma concentration of PF-05230907 (C_{\max}) was reached between 2 to 5 minutes post-dose and PF-05230907 concentration declined very rapidly thereafter. In all subjects except one (from the 5 $\mu\text{g}/\text{kg}$ dose group), plasma PF-05230907 concentration was non-detectable by 40 minutes after dosing. The terminal half-life was calculated for 3 and 5 $\mu\text{g}/\text{kg}$, which are 4.6 (coefficient of variation [CV] =8%) and 3.7 (CV=2%) minutes respectively. Exposure appeared to increase dose-proportionally, especially at the higher doses where PK can be characterized more accurately. The very fast clearance of PF-05230907 is consistent with the observations in non-clinical studies.

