1.6. Anticipated Risks and Safety Monitoring

Complete information for this compound may be found in the Single Reference Safety Document (SRSD), which for this study is the Investigator's Brochure.

Human experience with PF-05230907 is limited to Phase 1 Study B2341001. There are no identified adverse drug reactions to PF-05230907. Potential risks are based on clinical and toxicology data.

Possible risks for PF-05230907 include the potential for thromboembolic and ischemic complications and the potential for immunogenicity including, but not limited to, infusion reactions, anaphylaxis, and formation of ADA which may affect functions of endogenous FXa and FX. Although the possibility of ADA development is considered to be low to moderate, the perceived immunogenicity risk of PF-05230907 is considered to be high based on the severe consequence that the ADA may affect function of endogenous FXa and FX.

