If a subject withdraws after Day 8/discharge and prior to Day 43 or if antibody results at Day 43 are not yet available, the following assessments should be completed:

- Collect the following blood samples:
 - Immunogenicity sample collection (ADA, NAb, and FX activity) for shipment to a central vendor.
- Conduct the mRS.
- Conduct the NIHSS.
- Document birth control utilized through the protocol required 28 days after the single dose of investigational product for male subjects who are able to father children and are sexually active and at risk of pregnancy, see [Section 4.4](#).
- Monitoring of concomitant medications and treatments.
- Monitoring of serious adverse events.
- Collect appropriate health resource utilization information which includes: as applicable, date subject began out-patient rehabilitation and discharge date subject completed out-patient rehabilitation.

If a subject withdraws after Day 43 and prior to Day 91, the following assessments should be completed:

- Collect the following blood samples **only** if subject tested positive for antibody immune response to PF-05230907 at Day 43 (sites will be notified if a subject has evidence of a previous antibody immune response to PF-05230907):
 - Immunogenicity sample collections (ADA, NAb, and FX activity) for shipment to a central vendor.
- Conduct the mRS.
- Conduct the NIHSS.
- Collect appropriate health resource utilization information which includes: as applicable, date subject began out-patient rehabilitation and discharge date subject completed out-patient rehabilitation.

If the subject withdraws from the study, and also withdraws consent for disclosure of future information, no further evaluations should be performed, and no additional data should be collected. The sponsor may retain and continue to use any data collected before such withdrawal of consent.

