7.8. Triggered Requirements

Condition	Action
Subjects with previous evidence of an antibody immune response to PF-05230907 at Day 43 (sites will be notified if a subject has evidence of a previous antibody immune response to PF-05230907 as defined in Section 9.6.1).	Collect immunogenicity blood samples (ADA, Nab, and FX activity) at Day 91 for shipment to a central vendor.

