### **3.2.2. Immunogenicity Endpoint**

The immunogenicity endpoint includes anti-drug antibody (ADA), neutralizing anti-PF-05230907 antibody (NAb), and Factor X activity through Day 43 and/or Day 91 follow-up visit. Blood samples for this endpoint will be collected at the time points described in SoA and analyzed.

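### A continuing subject who misses the Day 43 antibody draw cannot be sampled at Day 91, yet can be counted as antibody-negative on a first-week sample

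*Protocol*

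**What the plan says.** Estimating how often subjects develop an antibody response is a secondary objective. SAP 3.2.2 defines the endpoint as ADA, NAb and "Factor X activity through Day 43 and/or Day 91 follow-up visit".

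Post-dose samples are drawn at Day 8 or discharge (on Day 4 if the subject leaves then) and at Day 43 ± 7 days. Three places restrict Day 91:

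- Schedule of Activities, footnote j: "ADA, NAb and FX activity to be collected at Day 91 only if subject tested positive for antibody immune response at Day 43".
- Protocol 6.3.2: sampling only "if subject tested positive for antibody immune response to PF-05230907 at Day 43".
- Protocol 7.8, where the trigger is: "Subjects with previous evidence of an antibody immune response to PF-05230907 at Day 43".

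Protocol 6.3 foresees that some subjects will not attend Day 43. If neither a clinic nor a remote visit is possible, "a telephone follow-up for collection of serious adverse events since the last visit should occur"; no replacement sample is mentioned. Protocol 6.4 is more generous to subjects who leave. Those who withdraw after Day 8/discharge and before Day 43, "or if antibody results at Day 43 are not yet available", are to give ADA, NAb and FX activity samples.

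On the analysis side, SAP 4.3.3 requires only one post-treatment measurement for entry to the immunogenicity set. SAP 6.2.2 then tabulates the number and percentage of subjects with a positive or negative response by dose group.

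**The concern.** The rule treats a missing Day 43 result in the same way as a negative one: both close Day 91 sampling. A subject who comes to Day 91 for the mRS and NIHSS is therefore left untested although present in the clinic. That subject's only post-dose antibody result dates from the first nine days and still places the subject in the denominator. A continuing subject can end up less well observed than one who withdraws.

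Protocol 1.6 states that "the perceived immunogenicity risk of PF-05230907 is considered to be high", because antibodies might impair endogenous FX and FXa, although it rates the likelihood of their development only low to moderate. FX activity is drawn with the same samples and is one route to a neutralizing-antibody classification in SAP 6.2.2, so it is lost too.

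**Working it through.** **Reproducing the plan's windows.** With hours = (day − 1) × 24 ± window, SAP Table 4 is recovered exactly:

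- Day 8: 168 ± 48 = 120 to 216 h (Day 6 to Day 10).
- Day 43: 1008 ± 288 = 720 to 1296 h (Day 31 to Day 55).
- Day 91: 2160 ± 288 = 1872 to 2448 h (Day 79 to Day 103).

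**The affected subject.** Follow a subject who is discharged between Day 4 and Day 8, does not withdraw, misses Day 43 and attends Day 91.

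- Last sample: Day 4 at the earliest, Day 8 + 1 = Day 9 at the latest.
- Day 91 visit under the protocol window: Day 84 to Day 98.
- Time in the study after the last antibody sample: at least 84 − 9 = 75 days, at most 98 − 4 = 94 days.
- SAP 4.3.3: one post-treatment sample, so the subject is in the set.
- SAP 6.2.2: if that sample was negative, nothing stops the subject counting as negative. SAP 5.3.2 allows a missing category, but a subject with one result is not obviously missing at subject level.

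A negative first-week result carries little information. In the first-in-human study the single responder was still negative at Day 15 (Protocol 1.3.2).

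**Size of the bias.** Let N be the number in the immunogenicity set and m the number with no sample after Day 8/discharge for this reason. If those m subjects have the same chance of response as the others, and responses are not yet visible in the first-week sample, then

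expected reported frequency ÷ frequency with full Day 43 sampling = (N − m) / N.

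SAP section 1 gives 21 enrolled. Taking N = 21 as an assumption:

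- m = 1: 20/21 = 95%.
- m = 2: 19/21 = 90%.
- m = 5: 16/21 = 76%.

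Neither document gives m; 1 to 5 is an illustrative range. Subjects who die after the early sample also stay in the denominator, but no sampling rule can reach them.

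**The separate gap in scheduled visits.**

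- Protocol windows: Day 9 to Day 36, so 36 − 9 = 27 days at the least. After a Day 4 discharge it is 36 − 4 = 32 to 50 − 4 = 46 days.
- SAP analysis windows: Day 10 to Day 31, so 21 days.

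The one human ADA response was positive at Day 29 only; "ADA results for the same subject on Day 1 (baseline), Day 15, Day 43, and the 6 month follow-up were negative". Day 29 lies inside the gap under either set of windows. At nominal times this trial would sample such a subject at Day 8 and Day 43 and find both negative.

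If all 37 exposed first-in-human subjects were tested, the rate is 1/37 = 2.7% (exact 95% interval 0.07% to 14.2%). At that rate the chance of at least one such responder among 21 is 1 − (36/37)^21 = 44%. The interval limits give about 1% to 96%, so a single case says little about how often this would happen.

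**The case against.** The best defence is that the affected group is small. Protocol 6.3 and 6.4 ask sites to make every effort, including transport, and Protocol 7 encourages remote visits, so a missed Day 43 draw should be uncommon. Protocol 6.4 asks for a sample from subjects who withdraw before Day 43. The endpoint is secondary and descriptive, and the one known response was weak, transient, not cross-reactive and non-neutralizing; the sponsor, investigator and data monitoring committee judged that it did not alter benefit and risk. All of this stands. It limits the size of the problem but supplies no sample for the continuing subject who misses Day 43.

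Several stronger readings are tempting, and the documents do not support them:

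- A reader might infer that nobody is sampled between Day 9 and Day 36, or that everyone without a Day 43 sample goes untested late. Protocol 6.4 contradicts both for subjects who withdraw in that interval. The gap is in scheduled visits.
- A reader might blame the Day 91 rule for missing a response like the one in the first-in-human study. That subject was negative at Day 43 and at 6 months, so open Day 91 sampling would not be expected to find it. Nor is the miss certain away from nominal times: status between Day 29 and Day 43 is unknown, and a draw on Day 36 might have been positive.
- A reader might think that a Day 8 positive with Day 43 missing lowers the frequency. If it meets the response definition in SAP 6.2.2, that subject is already a responder; only persistence goes unobserved.
- A Day 43 result still pending at Day 91 is possible but unlikely. The shortest in-window interval is Day 50 to Day 84, 34 days, and nothing in the documents suggests turnaround that slow.

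**Conclusion.** The concern holds for a defined group: subjects who remain in the study, miss the Day 43 draw including any remote visit, and attend Day 91. They have no antibody or FX activity sample after Day 4 to Day 9, yet can count as negative, so the bias in the reported frequency is downward. Its size is (N − m)/N. The illustrative 95% to 76% rests on an assumed 1 to 5 affected subjects out of 21, equal response chances, and no response visible in the first week.

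The interval from about Day 9 to Day 36 (Day 10 to Day 31 with SAP windows) is a limitation on what the estimate means. It does not follow from the Day 91 rule. The first-in-human case illustrates it and does not measure the effect of that rule. SAP 6.2.2 already summarizes assay results by visit, and SAP 3.2.2 does not claim a cumulative frequency, so what is missing is a clear description of the subject-level percentage. The MTD analysis is not touched.

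**What to change.** In Schedule of Activities footnote j, Protocol 6.3.2 and Protocol 7.8, keep the present trigger and add two: collect ADA, NAb and FX activity at Day 91 when no Day 43 sample or result is available, and when an earlier post-dose sample was positive and Day 43 is missing. The second shows persistence and does not change the frequency. A Day 91 sample recovers only responses still detectable then.

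In SAP 6.2.2, describe the subject-level ADA and NAb percentages as positivity at the sampled visits, not as cumulative frequency through Day 43. State that no visit was scheduled between about Day 9 and Day 36, and that a short-lived response in that interval could be missed.

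The cost is one extra tube at an already scheduled visit for a few subjects, plus a few sentences in the SAP. The immunogenicity statement becomes more modest. Enrollment ended at 21 subjects, so the sampling change may come too late for this trial and serve mainly a later protocol; the SAP wording can still be changed.
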